Acceptability and feasibility. We will collect data on participants' tDCS experience via a questionnaire, at the conclusion of tDCS treatment on a 0 (strongly disagree) to 10 (strongly agree) scale: 1) It was easy to prepare the device and accessories; 2) The device was unnecessarily complex; 3) The device was easy to use; 4) I felt the video conferences with a technical person were helpful; 5) I would imagine that most people would learn to use this device quickly; 6) The device was cumbersome to use; 7) I felt confident using the device; 8) I needed to learn a lot of things before I could get going with this device; 9) The effectiveness of the treatment increased over the course of treatment; 10) Overall, I felt that transcranial electrical stimulation treatment benefited me. Moreover, we will evaluate the presence and severity of possible side effects of treatment at the end of each session on a 0 (not at all) to 10 (highest degree) scale. By using open-ended questions, the participants will be asked whether they experienced any side effects, and they will then be asked specifically about tingling, itching sensation, burning sensation, pain at the stimulation site, fatigue, nervousness, headache, difficulty concentrating, mood change, and changes in vision or visual perception. If any side effects are reported, the degree of relatedness to the intervention will be assessed on a 5-point scale. This approach has been used in our previous study and frequently in other studies⁵⁸⁻⁶⁰. Regarding feasibility, we will calculate the percentage of participants who a) met the inclusion criteria, b) agreed to be randomly assigned, c) completed the full tDCS+MBI protocol, and d) attended the follow-up assessment.

6.3 Treatment conditions:

The Food and Drug Administration (FDA) has ruled that the aforementioned tDCS stimulator is a "non-significant risk" device, a requirement for Investigational Device Exceptions. For pain treatment, tDCS is typically delivered

PROTOCOL TITLE:

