15.0 Risks to Subjects*

15.1 No adverse events have been reported in relation to mindfulness-based intervention or tDCS. We have conducted several studies on tDCS and patients minimal side effects such as slight itching (present in 30% of people as reported by systematic reviews) or tingling on the scalp (present in 70% of people as reported in systematic reviews). Although we have not observed other side effects. Systematic reviews report the possibility of dizziness in 10% of people, nausea in 3% and headache in 11% of people. The Food and Drug Administration (FDA) has ruled that the aforementioned tDCS stimulator is a “non-significant risk” device, a requirement for Investigational Device Exceptions.

15.2 Patients may feel tired while completing questionnaires, but they can pause and resume at any time. Individual interviews and some items from questionnaires may allow emotions related to the experience of a major surgery to emerge. If psychological distress becomes obvious (verbatim or score on a questionnaire), the provider will be informed for follow-up and the patient will be encouraged to communicate with the clinic.

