18.0 Provisions to Monitor the Data to Ensure the Safety of Subjects*

PROTOCOL TITLE:

[name] has the primary responsibility for monitoring study research staff. Research team will receive training on the study design, recruitment and protocol. Weekly meetings will take place with study staff to ensure protocol adherence and monthly meetings with co-investigators to discuss any issues. Patients' experiences and any potential adverse events will be reviewed and discussed. Each treatment session will be remotely supervised via zoom and after each session any potential side effects will be investigated and documented by the research coordinator (see questionnaires), [name]. This monitoring will be continued after surgery for the remainder of the data collection (up to 1 month).

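### The prompted side-effect list leaves out dizziness and nausea, two of the five effects the protocol itself gives rates for, so ascertainment is uneven and these two may be under-counted

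*Protocol*

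**What the plan says.** Protocol 6.2, in the paragraph on acceptability and feasibility, collects the presence and severity of side effects at the end of each session on a 0-10 scale. Questioning has two steps. The first is open: "By using open-ended questions, the participants will be asked whether they experienced any side effects". The second is a fixed list put to them by name: "tingling, itching sensation, burning sensation, pain at the stimulation site, fatigue, nervousness, headache", followed by "difficulty concentrating, mood change, and changes in vision or visual perception". That makes ten prompted effects. Any reported effect is then rated for relatedness on a 5-point scale. The schedule in section 4.0 marks the side-effects questionnaire at five preoperative points.

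Protocol 15.1 gives rates for five effects of stimulation. Two are local: "slight itching (present in 30% of people as reported by systematic reviews" and "tingling on the scalp (present in 70% of people as reported in systematic reviews", each parenthesis closing there. The other three come in one sentence: "Systematic reviews report the possibility of dizziness in 10% of people, nausea in 3% and headache in 11% of people".

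Protocol 18.0 adds that sessions are supervised by video and that "after each session any potential side effects will be investigated and documented by the research coordinator (see questionnaires", again with the parenthesis closing there.

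Neither the analysis text in Protocol 17.1 nor the SAP describes an analysis of side effects.

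**The concern.** The risk section and the questionnaire description do not match. Headache and dizziness have almost the same cited rate (11% and 10%), yet one is asked about by name and the other is not. The protocol gives no reason for the difference, and it does prompt for effects that section 15.1 does not mention, such as nervousness, mood change and visual change.

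The difference affects how the data can be read. A prompted item can return an explicit zero. For an unprompted symptom, silence may mean that it was absent or that it was not mentioned. A table setting dizziness and nausea beside headache, itching and tingling would mix two methods of ascertainment. The trial's own check on the 10% and 3% figures would also be weaker than its check on the other three.

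Side-effect data matter here because section 6.2 collects them under acceptability and feasibility, which section 1.0 names as the primary objective, and because the stimulation is self-administered at home.

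**Working it through.** **Step 1: compare the two lists.**

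| Effect with a rate in 15.1 | Cited rate | Prompted in 6.2? |
|---|---|---|
| Tingling | 70% | Yes |
| Itching | 30% | Yes |
| Headache | 11% | Yes |
| Dizziness | 10% | No |
| Nausea | 3% | No |

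Three of five are prompted and two are not.

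**Step 2: look for another route of capture.** The open question in 6.2 can pick up either symptom. The inquiry in 18.0 refers the reader to the questionnaires, so the documents do not show it to be a separate instrument. On the text, dizziness and nausea depend on spontaneous report.

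**Step 3: inputs for a sense of scale.** The 10% and 3% are cited background rates with no inputs to reproduce. The other inputs are:

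- n = 20 in the active arm: 40 completers (section 12.1) at 1:1 allocation (section 6.1), 40 / 2 = 20.
- p = 0.10 for dizziness and 0.03 for nausea (section 15.1), taken as per-person rates that apply to the active arm.
- s = the share of true cases volunteered to the open question. The documents do not give it; a range of 25% to 100% is assumed.

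**Step 4: full reporting (s = 1).** Expected cases = n × p. The chance of seeing at least one = 1 − (1 − p)^n.

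- Dizziness: 20 × 0.10 = 2.0; 1 − 0.90^20 = 0.88.
- Nausea: 20 × 0.03 = 0.6; 1 − 0.97^20 = 0.46.

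These figures show what prompting with complete reporting would yield. They do not measure what is lost.

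**Step 5: partial volunteering.** Expected recorded cases = n × p × s; chance of at least one = 1 − (1 − p × s)^n; shortfall = n × p × (1 − s).

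| s (assumed) | Dizziness: expected | at least one | shortfall | Nausea: expected | at least one | shortfall |
|---|---|---|---|---|---|---|
| 100% | 2.0 | 0.88 | 0 | 0.60 | 0.46 | 0 |
| 75% | 1.5 | 0.79 | 0.5 | 0.45 | 0.37 | 0.15 |
| 50% | 1.0 | 0.64 | 1.0 | 0.30 | 0.26 | 0.30 |
| 25% | 0.5 | 0.40 | 1.5 | 0.15 | 0.14 | 0.45 |

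Over the assumed range the expected shortfall is 0 to 1.5 dizziness cases and 0 to 0.45 nausea cases. The absolute numbers are small, but with so few expected events one or two unmentioned cases can decide whether a symptom is reported as seen at all.

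**The case against.** The strongest reply is that participants are already asked. The open question comes before the prompts, each session is supervised live, and staff inquire soon after it ends, on up to five occasions. A participant who felt dizzy or sick has a clear opportunity to say so, and the severity and relatedness scales are not restricted to prompted items. The protocol also says that its approach was used in an earlier study by the team and in others, and nothing in it requires the checklist to mirror the risk section. The form itself is not in the documents and may carry more items than section 6.2 describes. No planned analysis compares one symptom's rate with another's.

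Much of this stands, and it rules out three stronger readings that a reader might infer:

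- **That the two effects will be under-counted.** The open question can capture every case. Only the possibility of under-counting follows from the text.
- **That the 88% and 46% measure the harm.** They describe full reporting. The loss depends on the volunteered share, which the documents do not give, and zero loss is within the assumed range.
- **That the comparison of active with sham is biased.** The same questioning is described for all participants, so the text implies no difference in ascertainment between arms.

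What does not stand is the suggestion that the gap is closed. The protocol adds named prompts after its open question, which suggests that it does not rely on the open question alone, and section 18.0 points back to the same questionnaires. If the form does include the two symptoms, section 6.2 should say so.

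**Conclusion.** The point holds as a minor one. Two of the five effects with rates in section 15.1 are left to spontaneous report while the other three are prompted, so ascertainment is uneven across symptoms. Dizziness and nausea may be under-counted, by an amount that cannot be derived from the documents. The illustrative shortfall of up to 1.5 and 0.45 cases among 20 active participants rests on three assumptions: that the cited rates apply to the active arm, that they are per-person rates, and that between 25% and 100% of cases are volunteered. The conclusion about uneven ascertainment needs none of these; it rests on the text of sections 6.2 and 15.1, with the caveat that the form itself could not be checked.

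**What to change.** Add dizziness and nausea to the prompted list in Protocol 6.2 and on the form, at each session and in both arms, using the 0-10 severity scale and the 5-point relatedness scale already in place. If the form already has them, amend section 6.2 to say so.

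The SAP, dated October 2025, is written in the past tense, so data collection may be over. In that case, state in the report which effects were prompted and which were volunteered, label dizziness and nausea as volunteered, and do not present their rates, or an absence of cases, as equivalent to prompted rates. The form change would then serve a later trial.

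The cost is two extra items per session, or a sentence or two of disclosure in the report.

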7.0 Data and Specimen Banking*

7.1 *Data (questionnaires, sociodemographic and clinical info) will have identifiers removed and banked indefinitely. Data will be available to research team, PI, RA, statistician. Data will be stored on a password-protected computer. The computer will be stored in a locked room.*

8.0 Sharing of Results with Subjects*

8.1 *Data will be released to participants upon request and approval by PI (HIPAA). De-identified datasets will be available to the scientific community upon request (depending on the journal policy in which results will be published).*

9.0 Study Timelines*

PROTOCOL TITLE:

- *The duration of an individual subject's participation in the study: 1 month*
- *The duration anticipated to enroll all study subjects: 6 months*
- *The estimated date for the investigators to complete this study: 7 months*

10.0 Inclusion and Exclusion Criteria*

Inclusion criteria: elective unilateral knee total replacement, (4) mentally capable of reading, giving consent and following instructions, (5) being able to answer questions in English, (6) not pregnant. Exclusion criteria include: (1) history of brain surgery, brain tumor, seizure, stroke, or intracranial metal implantation, (2) systemic rheumatic disorders, including rheumatoid arthritis, systemic lupus erythematosus, and fibromyalgia, (3) alcohol/substance abuse, (4) current use of sodium channel blockers, calcium channel blockers and NMDS receptor antagonists, (5) hospitalization within the preceding year for psychiatric illness, and (6) no access to a device with internet access that can be used for secure videoconferencing for real-time remote supervision.

Following populations will not be included:

- *Adults unable to consent*
- *Individuals who are not yet adults (infants, children, teenagers)*
- *Pregnant women*
- *Prisoners*

11.0 Vulnerable Populations*

11.1 N/A

12.0 Local Number of Subjects

12.1 N=40 (completers)

13.0 Recruitment Methods

An experienced research assistant (RA) and/or the PI will be responsible of participants' recruitment and informed consent procedures.

The research coordinator ([name]) will review the preoperative clinic schedule. The individual will conduct a pre-screening of potentially eligible participants (see attached HIPAA waiver). A clinician (Registered nurse, [name]) will introduce the study to potential participants at their preoperative visit by using a flyer. If the individual agrees to learn more, the PI or RA will enter the room to discuss study, answer questions, sign the consent and schedule the visit to the lab. Before any in-person interaction, COVID-19 screening will be conducted.

PROTOCOL TITLE:

The PI and RA are fully vaccinated, they will use the CDC self-checker tool and wear a mask at all times, as well as respect the clinic's current policies. Patients usually receive a COVID screening before starting their visit at the clinic and the clinician will inform them about FSU COVID-19 precautions and distribute the FSU Information sheet.

13.1 Source of subjects: community/outpatient clinics

13.2 Participants in both groups will receive gift cards of \$100 at the end of the study.

14.0 Withdrawal of Subjects*

14.1 Participants will be withdrawn without their consent if complications occur during their postoperative recovery and they need to be re-admitted to the hospital.

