2.0 Objectives*

2.1 The goal of this project is to assess the preliminary feasibility, acceptability, and efficacy of self-administered preoperative tDCS+MBI in older adults (50+) undergoing TKR. The central hypothesis is that combined preoperative tDCS+MBI will decrease postoperative analgesic consumption, postoperative clinical pain severity, as well as preoperative pain-related cortical response. We will accomplish three aims using a randomized controlled trial.

2.2 *Hypotheses:*

To determine the effects of 5, 20-minute preoperative self-administered tDCS sessions combined with brief MBI on analgesic medication consumption following TKR

Hypothesis 1: participants receiving preoperative active tDCS+MBI will show reduced postoperative analgesic consumption.

To determine the effects of 5, 20-minute preoperative self-administered tDCS sessions combined with brief MBI on postoperative pain severity following TKR

Hypothesis 2: participants receiving preoperative active tDCS+MBI will show reduced postoperative pain intensity and pain interference with physical and emotional function 5 days and 1 month after TKR.

To explore the effects of 5, 20-minute preoperative self-administered tDCS sessions combined with brief MBI on preoperative endogenous pain modulation

PROTOCOL TITLE:

Hypothesis 3: participants receiving preoperative active tDCS+MBI will show improved preoperative endogenous pain modulation.

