4.0 Study Endpoints*

- 4.1 Measures will be taken by a research assistant via a telephone interview using a Qualtrics® survey. Outcome measures will be taken at 4 time points: 1) baseline (before preoperative active/sham tDCS+MBI), 2) after 5 sessions of preoperative active/sham tDCS+MBI, 3) after surgery, and 4) 1 month after surgery (see table below)
- 4.2 Primary endpoint: Analgesic consumption. The dose of every opioid received within 5 days postoperatively will be transcribed and converted into standardized parenteral morphine equivalents using the Centers for Disease and Control Prevention Guidelines on opioids⁴². A total in milligrams will be calculated for each day and means will be obtained for all groups.
- 4.3 Secondary endpoints: pain severity (numeric rating scale 0-100), pain interference with activities (numeric rating scale 0-10), depression and anxiety (PHQ-4), pain catastrophizing (Pain Catastrophizing Scale), multimodal quantitative sensory testing (QST) including heat pain (e.g., threshold, tolerance), pressure pain threshold, punctate mechanical pain (e.g., suprathreshold ratings and temporal summation), and Conditioned Pain Modulation (CPM), acceptability and feasibility

Day/month	B	Preoperative phase	Postoperative phase
-----------	---	--------------------	---------------------

PROTOCOL TITLE:

		Day 1	Day 2	Day 3	Day 4	Day 5	Day 1	Day 2	Day 3	Month 1
Medical History Questionnaire	X									
Analgesic consumption (primary outcome)							X	X	X	X
Clinical Pain severity (secondary outcome)										
NRS	X					X			X	X
BPI	X					X			X	X
PHQ-4	X					X			X	X
PCS	X					X			X	X
Pain-related Cortical Response (secondary outcome)										
QST measures	X					X				
Acceptability and feasibility										
tDCS + MBI experience questionnaire						X				
Side effects questionnaire		X	X	X	X	X				

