6.0 Procedures Involved*

6.1 This study will use double-blind randomized sham-controlled design with an allocation ratio of 1:1 with repeated measures at 4 time points. Participants will be randomly assigned to one of 2 arms as follows: 1) preoperative active tDCS+MBI or 2) preoperative sham tDCS+MBI. Participants will be recruited at their preoperative visit (see letter of collaboration). A clinician (registered nurse or surgeon) or a research coordinator from the clinic will review the preoperative

PROTOCOL TITLE:

clinic schedule, conduct a pre-screening of potentially eligible participants, and introduce the study to potential participants at their preoperative visit by using a flyer. If the individual agrees to learn more, the PI or RA ([name]) will enter the room to discuss study, answer questions and sign the consent. If they agree to participate, after signing the consent, they will be invited to come to the brain stimulation laboratory (FSU innovation park) where a baseline assessment will be done before randomization by the RA or lab research coordinator ([name]). The tDCS device along with instructions will then be provided. The baseline visit will take approximately 2 hours. The preop procedures will be as follows with T = day of surgery:

T-7: Recruitment/Consent

T-6: Baseline lab measurements & tDCS fitting and training

T-5: AM & PM remote tDCS/MBI

T-4: AM & PM remote tDCS/MBI

T-3: AM remote tDCS/MBI + Post-intervention lab measurement & collect tDCS equipment

6.2 Measures:

Usual sociodemographic variables (i.e., age, sex, civil status, living conditions, education level, and employment status) will be assessed. Relevant medico-surgical information during hospitalization will be collected: type of surgery, postoperative complications, and current involvement in a rehabilitation program. The presence of chronic pain before surgery will also be documented.

Outcome measures will be taken at 4 time points: 1) baseline (before preoperative active/sham tDCS+MBI), 2) after 5 sessions of preoperative active/sham tDCS+MBI, 3) after surgery, and 4) 1 month after surgery. Table 1 gives an overview of all measures for the preoperative and postoperative phases.

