16.0 Potential Benefits to Subjects*

16.1 Based on previous studies, participants may use less opioids and experience less pain and anxiety. This reduction may allow for a better recovery and return to activities.

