17.0 Data Management* and Confidentiality

17.1 The protocol will favor an intention-to-treat approach for the analysis of results.

PROTOCOL TITLE:

Data analysis will be performed with R (Vienna, Austria) version 4.1+. Baseline demographic information will be summarized using descriptive statistics. Continuous variables will be summarized with means and standard deviations. Categorical variables will be summarized with counts, proportions, and medians (interquartile range). The distribution of all variables will be examined before any analysis, using appropriate statistical tests like Shapiro's test for normality checking. If the assumption of normality is not met, equivalent non-parametric approaches or data transformation will be employed. The multiple testing problem will be accounted for using Bonferroni correction. All testing will be two-sided and 0.05 will be used as the familywise significance level. If needed, statistical analysis will also be conducted after controlling for baseline demographics and clinical characteristics (e.g., age, sex, and race).

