For Aim 1, analgesic consumption measured on 3 consecutive days will be summarized into one number for each subject. Two-sample t-test (or non-parametric alternative) will be employed to determine the significance of the difference between the active and the sham tDCS+MBI groups. Multivariate linear regression will be further employed to account for potential confounding factors, including selected baseline demographics and clinical characteristics (e.g., age, sex, race, and body mass index). For Aim 2, we will conduct multivariable regression analysis to compare the change in clinical pain intensity (NRS, BPI, PHQ-4, PCS) from baseline to Day 3 in the postoperative phase after controlling for baseline and other confounding factors (e.g., age, race, sex, baseline NRS, consumption of pain medications). We will also determine whether the improvement conferred by active tDCS+MBI can be sustained by comparing the clinical pain intensity changes from baseline to 1 month between the active and the sham groups. We will also conduct sex-stratified analysis and explore whether there exists sex difference in these effects. For Aim 3, the QST dataset for endogenous pain modulation will be analyzed using multivariate linear regression for changes in each of the QST measures against potential confounding factors, and backward stepwise variable selection will then be performed to identify the parsimonious model structures. Spearman rank-order correlation will be used to quantify the association between changes in each of the QST measures and the changes in clinical pain intensity (NRS).

17.2. The PI, RA and research coordinator received the CITI training. Data will be de-identified and a code will be assigned to each participant.

17.3 Data entry will be validated at random.

17.4 Data (questionnaires, sociodemographic and clinical info) will have identifiers removed and banked for a minimum of 3 years per Federal regulations. Deidentified data will be available to research team: PI, co-I ([name] and [name]), RA, statistician ([name], CON). Data will be stored on a password-protected computer. The computer will be stored in a locked room. Any data collected online will be stored on an encrypted data server at the CON. Any downloaded data will be stored on a password protected computer. The RA supervised by the PI will be responsible for data receipt. [name] and [name] will assist with results interpretation.

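### Section 14.1 withdraws readmitted participants when no study treatment is left to stop, so it can only cost 1-month and safety data, against the favored intention-to-treat approach

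*Protocol*

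**What the plan says.** The rule is in Protocol section 14.1: "Participants will be withdrawn without their consent if complications occur during their postoperative recovery and they need to be re-admitted to the hospital". It does not separate stopping treatment from stopping follow-up. It says nothing about retaining data or completing the 1-month assessment.

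Other sections bear on it:

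- **Treatment schedule.** In section 6.1, with T the day of surgery, the final preoperative entry reads "T-3: AM remote tDCS/MBI + Post-intervention lab measurement & collect tDCS equipment". Section 6.3 likewise places all stimulation before surgery.
- **Mode of assessment.** Section 4.1: "Measures will be taken by a research assistant via a telephone interview". Section 24.1 makes assessment remote apart from the baseline visit and one preoperative follow-up visit.
- **Analysis principle.** Section 17.1: "The protocol will favor an intention-to-treat approach for the analysis of results".
- **1-month outcomes.** Hypothesis 2 (section 2.2) covers pain intensity and "pain interference with physical and emotional function 5 days and 1 month after TKR". The Aim 2 analysis in section 17.1 tests sustained benefit by "comparing the clinical pain intensity changes from baseline to 1 month between the active and the sham groups".
- **Complications and safety.** Section 6.2: "Relevant medico-surgical information during hospitalization will be collected: type of surgery, postoperative complications". Section 18.0 continues monitoring after surgery while data are being collected, up to 1 month.
- **Feasibility and sample size.** Follow-up attendance is one of four feasibility percentages in section 6.2. Section 12.1 counts the 40 participants as completers and gives no replacement rule.
- **SAP.** It plans change-score tests and a mixed effects model. It contains no intention-to-treat statement and no rule for participants withdrawn under 14.1.

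**The concern.** A withdrawal rule normally protects a participant from further exposure to study treatment. Here none remains after surgery, so the rule can act only on data collection, and it does so even for a participant willing to continue.

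The trigger occurs after randomisation and is plausibly related to outcome. Section 16.1 expects less opioid use and less pain, and adds: "This reduction may allow for a better recovery and return to activities". If treatment influences recovery, the participants removed are not a random subset.

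The 1-month pain and interference outcomes, the follow-up attendance percentage and the later course of the gravest events are mainly exposed. The 5-day opioid data may be partly or wholly intact, depending on when readmission occurs. The QST and experience-questionnaire data are preoperative and unaffected.

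**Working it through.** The plan has no figure of its own to reproduce: it gives no readmission rate, no SD for the 0-100 NRS and no pain excess for readmitted patients. These three are assumptions below. From the documents come N = 40 and 1:1 allocation, hence 20 per arm. I take 40 as the number randomised.

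**1. Timeline (section 6.1).** Sessions: 2 on T-5, 2 on T-4 and 1 on T-3, so 2 + 2 + 1 = 5, all before surgery. Treatment remaining at a postoperative readmission: none.

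**2. How many are affected.** Expected number = 40p; chance of at least one = 1 - (1 - p)^40.

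| Assumed p | Expected | At least one |
|---|---|---|
| 2% | 0.8 | 0.554 |
| 5% | 2.0 | 0.871 |
| 10% | 4.0 | 0.985 |

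**3. Feasibility.** Highest possible attendance with m withdrawals = (40 - m)/40: 97.5% for m = 1, 95% for m = 2, 90% for m = 4. This needs no assumption about pain.

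**4. Shift in the 1-month arm difference.** If readmitted patients score D points higher in either arm, dropping them shifts the difference by D × (k_sham - k_active)/20.

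- Net one extra withdrawal in an arm: 0.5, 1.0 and 1.5 points for D = 10, 20 and 30.
- Net two: 1.0, 2.0 and 3.0 points.
- Standard error of the difference = SD × √(2/20): 6.3 for SD 20 and 9.5 for SD 30.

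**5. Uneven splits by chance at equal risk.**

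- Two withdrawals in the same arm: 2·C(20,2)/C(40,2) = 0.487.
- Four splitting 3-1 either way: 2·C(20,3)·20/C(40,4) = 0.499.
- Four splitting 4-0 either way: 2·C(20,4)/C(40,4) = 0.106.

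Imbalance alone is therefore not evidence of bias. The shift is systematic only if treatment affects the number or severity of readmissions.

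**6. What the SAP methods recover.** A change-score test to 1 month needs the missing value. The mixed model retains the Day 1 value, and its recovery per withdrawn participant is roughly b × E1, where b is the slope of the 1-month score on the Day 1 score and E1 is the Day 1 excess. With an assumed b = 0.5 and a true 1-month excess of 30:

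- E1 = 0: 0.5 × 0 = 0 of 30 recovered.
- E1 = 10: 0.5 × 10 = 5 of 30, or 17%.

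A complication arising after Day 1 need not show in the Day 1 score, so the model may repair little of the loss.

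**The case against.** The strongest reply is that section 14.1 says only that participants are withdrawn. It does not say that follow-up stops or that data are discarded, and section 18.0 makes no exception for withdrawn participants. Intention-to-treat is only favored, and an analysis of everyone in their randomised arm with some values missing remains possible. The study must know of a readmission to apply the rule, so the event itself is not hidden.

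The numbers are also small. Even four withdrawals all in one arm with a 30-point excess give 30 × 4/20 = 6.0 points, below the smallest standard error of 6.3. The outcome is secondary, the trial is a pilot, and no attendance threshold is set. The recovery figures rest on assumed inputs and on a postoperative Day 1 score that the SAP uses but the protocol's schedule does not list for the NRS. If 40 means completers, the attendance ceilings become 40/41 = 97.6% and 40/44 = 90.9%.

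Much of this stands as qualification: that withdrawal ends follow-up is an inference, the numerical effect is small, and no document shows that such a withdrawal occurred. It does not remove the point. With treatment already over, ending data collection is the only function the rule can have. A formally possible intention-to-treat analysis does not justify creating missing data by rule. Knowing that a readmission happened is not the same as following its course, since section 6.2 records complications during hospitalisation and later capture depends on continued follow-up. The choice of denominator changes the ceilings by less than one percentage point.

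**Conclusion.** The concern holds and should be fixed. The wording and timeline are clear: the rule takes effect after treatment has ended, is triggered by a post-randomisation event plausibly linked to outcome, and works against both the favored analysis principle and the planned monitoring. Telephone assessment leaves no evident logistical need for it.

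The case rests on avoidable, selective loss, not on a large bias. The likely cost is a few 1-month records, a feasibility percentage lowered by rule and not by participants' behaviour, and incomplete follow-up of the most serious events. The counts depend on the assumed 2% to 10% readmission rate. The NRS shift depends further on the assumed excess and SD, and is well below sampling error for a net one or two withdrawals. Confidence is high that the rule conflicts with the rest of the plan; how many participants it affects cannot be known from the documents.

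**What to change.** If follow-up is still open, amend section 14.1 so that a readmission is recorded as an adverse event and the participant stays in telephone follow-up and in the intention-to-treat analysis unless consent is withdrawn. State the sample size in section 12.1 as the number randomised. This takes one or two sentences and about 1 to 4 telephone calls.

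The SAP is written in the past tense, so data collection may be finished. In that case:

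1. Analyse all randomised participants with the data already collected.
2. Report 14.1 withdrawals by arm and timing.
3. Keep them in the feasibility denominators of section 6.2, shown separately from voluntary non-attendance.
4. Add a sensitivity analysis for their missing 1-month outcomes, for example the mixed-model estimate with 0, 10, 20 and 30 NRS points added for withdrawn participants.

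That costs one participant-flow row per arm and one extra analysis. The downsides are slightly more variable 1-month data, some readmitted participants who are harder to reach, and a little more analysis work. The change concerns data collection and analysis only, not clinical care.
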